1.1. Study Design and Patient Selection

This study was designed as a randomized, double-blind placebo-controlled trial to assess the effect of allopurinol administration in reducing tubular damage, vascular dysfunction and focal zone biophysical changes in the kidney due to ESWL.

Patients were randomly assigned to the intervention and placebo groups in this clinical study. The study group was formed of patients with kidney stone who undergo ESWL.

1.2. Process and Intervention

Patients with kidney stones who will undergo ESWL were randomized into 2 groups. Group 1 was given allopurinol, and group 2 was given a placebo. Allopurinol 300 mg was administered orally for a total of 3 days, starting from the day before ESWL. Malondialdehyde (MDA), nitric oxide (NO), kidney injury molecule-1 (KIM-1) in urine were measured by technique quantitative double antibody sandwich direct ELISA before ESWL, continued two hours, and 24 hours after ESWL. Changes in the interlobar artery resistive index (RI) were assessed together with measurements of shear wave velocity (SWV) values in the renal focal zone before ESWL, followed by two weeks, and four weeks after ESWL.

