1.4. Sample Size

The Population of the study consisted of patients with kidney stones who will undergo ESWL. The sample size was calculated based on the statistical diagnosis of the study which is, comparative analysis of independent two groups. A total of 70 subjects were planned to be included in the study, 35 of which were intervention while the rest were placebo. Patients were randomly assigned to both groups in this study.

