1.5. Ethical Approval

Approval for the study was granted by the Research Ethics Committee Faculty of Medicine, Udayana University (Number: 1637/UN14.2.2.VII.14/LT/2020). Verbal and written informed consent was obtained from all subjects in the study.

Author Contributions

Conflict of Interests

The Authors have no conflict of interests to declare

Acknowledgements

The authors thank all those participated in this study.

Financial Disclosure

STATISTICAL ANALYSIS PLAN (SAP)

Data collected in this study were analysed statistically using SPSS for Windows software 25. Data were analysed by descriptive statistics to describe the characteristics of the subjects based on the treatment group and presented in the form of a distribution table. The compatibility of the variables on the numerical data scale uses the average comparison with the independent t-test. The categorical-scale variables used the proportion comparison with chi-square test. The limit value of significance was set at 0.05. The normality data assessment in this study is based on the central limit theorem, where the sample size in each group more than 30 makes the z distribution close to the t distribution and the data will be normally distributed. Bivariate and Multivariate analyses were performed using repeated measure ANOVA to control covariates. The value of the limit of significance is set to 0.05.

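### Does starting study drug the day before ESWL, without saying whether the pre-ESWL measurement precedes the first dose, require a change to the plan?

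*Combined protocol and SAP*

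**What the plan says.** Section 1.1 gives the aim as the effect of allopurinol in "reducing tubular damage, vascular dysfunction and focal zone biophysical changes in the kidney due to ESWL".

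Section 1.2 sets the dosing: "Allopurinol 300 mg was administered orally for a total of 3 days, starting from the day before ESWL". The three urine markers "were measured by technique quantitative double antibody sandwich direct ELISA before ESWL, continued two hours, and 24 hours after ESWL". For the resistive index the wording is "Changes in the interlobar artery resistive index (RI) were assessed". The shear wave readings share that schedule, with one pre-procedure set and later ones at two and four weeks; the first is described as "measurements of shear wave velocity (SWV) values in the renal focal zone before ESWL". No section ties a pre-procedure measurement to the first dose or to randomization, and none defines a baseline.

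The SAP has two relevant sentences. One reads "The compatibility of the variables on the numerical data scale uses the average comparison with the independent t-test", which is most naturally a check that the groups are comparable. The other reads "Bivariate and Multivariate analyses were performed using repeated measure ANOVA to control covariates". Neither says whether the pre-ESWL value is a repeated level, a covariate or only a descriptive characteristic.

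**The concern.** In many trials the last measurement before the procedure is also the last before treatment. Here the dosing schedule separates the two. A sample taken before the first tablet and one taken on the morning of ESWL, after a day of drug, both fit the text.

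Randomization balances pre-dose values in expectation. It does not protect a value that treatment may already have shifted. If the reference is post-dose, a group difference in it could be an early drug effect and not chance. Subtracting or adjusting for it would then remove part of the drug's total effect. With 35 subjects per arm, losing a sizeable part of the effect could turn a detectable difference into a missed one.

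**Working it through.** **Timing.** Section 1.2 gives 3 days of drug, the first being the day before ESWL. Taken as consecutive (an assumption), these are days -1, 0 and +1, so 1 of 3 precedes the ESWL day. Each of the 5 measures has 1 value before the procedure and 2 after it.

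**What each analysis estimates.** Let b be the group difference already present in the pre-ESWL value and d the difference at each later time. A single d is a simplification, since RI and SWV are read two and four weeks later, after dosing has ended. Let rho be the correlation between time points.

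| Analysis | Group difference estimated | If b = 0 |
|---|---|---|
| Change from pre-ESWL (group-by-time contrast) | d - b | d |
| Adjusted for pre-ESWL value | d - rho × b | d |
| Post-ESWL values only | d | d |
| Average over all three times | (2d + b)/3 | 2d/3 |

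Three things follow.

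- If the value is pre-dose, b = 0 and the first three rows agree.
- If the value is post-dose, the first row still answers a proper question: how much the groups differ in the rise that follows ESWL. That matches the aim in section 1.1.
- The total effect of allocation is d. The third row estimates it from randomized groups with no reference value, so a pre-dose sample is not required for it.

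If allopurinol has no effect at all, b = d = 0, and every row is zero whenever the sample was taken. The timing therefore cannot create a false effect of treatment.

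**Could it matter for power?** The documents have no figure to reproduce. Section 1.4 gives 70 subjects, 35 per arm, without power, effect size or standard deviation (SD). As an illustration only, assume 80% power and two-sided 0.05. The detectable difference is (1.960 + 0.842) × sqrt(2/35) = 2.802 × 0.239 = 0.67 SD. Assume also rho = 0.5, and that a fraction f of the effect, in the same direction, is already present before ESWL.

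- Change score: SD = sqrt(2 × (1 - 0.5)) = 1, and power = Phi(2.80 × (1 - f) - 1.96). This gives 80%, 56% and 29% at f = 0, 0.25 and 0.50.
- Adjusted: SD = sqrt(1 - 0.25) = 0.866, and power = Phi((2.80/0.866) × (1 - 0.5f) - 1.96). This gives 90%, 81% and 68%.
- One post-ESWL value only: Phi(2.80 - 1.96) = 80% at every f.

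The 0.67, the 0.5, f and its sign are all assumed; none is in the documents.

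**Would a different main analysis be better?** Compare the mean of two post-ESWL values with and without adjustment, 35 per arm, equal variances and correlations. The unadjusted variance is (1 + rho)/2 and the adjusted variance is (1 + rho)/2 - rho². The 95% half-width is t × sqrt(variance × 2/35), with 68 and 67 degrees of freedom (t about 2.00 in both).

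| Assumed rho | Unadjusted | Adjusted | Ratio |
|---|---|---|---|
| 0.3 | 0.385 | 0.357 | 1.08 |
| 0.5 | 0.413 | 0.337 | 1.22 |
| 0.7 | 0.440 | 0.286 | 1.54 |

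Half-widths are in SD units. Dropping the pre-ESWL value as a precaution would widen the interval by 8% to 54%, to guard against a shift for which the documents give no evidence.

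**The case for a change.** The best case for acting is that clarification is cheap. A few sentences would state the timing and the role of the value, and one extra table would cover the post-dose case. No samples, scans or visits would be added. Section 1.1 speaks both of the effect of giving allopurinol and of damage due to ESWL, so a reader could take either as the target. And even with b = 0, averaging over all three times gives 2d/3 and not d, so the role of the pre-ESWL value matters whatever the timing.

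The first part stands as a courtesy to readers: timing relative to the first dose belongs in the report, as far as records allow. It does not show a fault in the plan, because the sentences would be blanks for the sponsor to fill in. Reporting timing by group also needs recorded dose and sampling times, and the documents do not say these were kept.

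The averaging point does not depend on when the drug was started. Section 1.2 lists the pre-ESWL value first in each series of three, and the SAP names repeated measures ANOVA. The ordinary reading is therefore a repeated level, with the group-by-time contrast carrying the treatment question. That contrast gives d when b = 0. Use of the value as a covariate is possible, since the SAP does not name its covariates, but it is the less natural reading.

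**Conclusion.** The text leaves open whether the pre-ESWL values precede the first dose. That is a missing detail, not a defect that makes the planned analysis wrong. Harm would need two things together: sampling after the first dose, and a drug effect on the marker before any shock wave. The documents support neither. For RI and SWV, any shift within a day of dosing may be negligible, so the practical question is mainly about the three urine markers.

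The size of b and its sign are unknown, so no loss can be put on the trial. The power figures show only that a large early effect would matter if the total effect were sought through a change score. For the rise due to ESWL, either timing is acceptable. For the total effect of allocation, the post-ESWL values already planned suffice. This rests on two readings: that the aim in section 1.1 is chiefly the damage caused by the procedure, and that the pre-ESWL value is the first repeated level. An analyst with the sampling records can settle the timing when reporting, and no change to the plan is called for.

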1.3. Safety Evaluation

If there was any drug side effects or serious adverse events(SAE), the subjects were reported to the ethics committee as soon as possible, less than 24 hours from the first time they were discovered, and actions were carried out as quickly as possible until the series of events ends. SAE was written in detail on the SAE form, including the following; when it was first discovered, the manifestation of the incident, the conditions before the incident, the handling of the event, and the outcome.

If the subject experiences side effects such as allergic reactions (redness of the skin, swelling of the eyes or mouth) and severe gastrointestinal disturbances (vomiting, diarrhea), the subject will be excluded from the analysis. The subject will also be excluded from the analysis if the subjects experience complications related to ESWL

procedure such as ureteral obstruction, pain (VAS > 5), or there were signs of infection. Subjects will be evaluated when visiting the hospital according to schedule, telephone contact, or by making a home visit.

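### Randomised subjects who have side effects or ESWL complications are dropped from the analysis, so the groups compared need not be comparable as randomised

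*Combined protocol and SAP*

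**What the plan says.** Section 1.3 (Safety Evaluation) contains two exclusion rules. The first concerns side effects, with allergic reactions and gastrointestinal upset as examples: "severe gastrointestinal disturbances (vomiting, diarrhea), the subject will be excluded from the analysis". The second concerns the procedure: "The subject will also be excluded from the analysis if the subjects experience complications related to ESWL", continuing "procedure such as ureteral obstruction, pain (VAS > 5), or there were signs of infection". Both lists are introduced as examples, so neither is closed. Neither rule has a time limit or is tied to a particular outcome.

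Section 1.2 fixes the order of events: "Patients with kidney stones who will undergo ESWL were randomized into 2 groups", and allopurinol "was administered orally for a total of 3 days, starting from the day before ESWL". Urinary MDA, NO and KIM-1 are complete at 24 hours. RI and SWV are measured before ESWL, "followed by two weeks, and four weeks after ESWL".

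On numbers, section 1.4 states: "A total of 70 subjects were planned to be included in the study, 35 of which were intervention while the rest were placebo". It mentions no allowance for exclusions. The SAP plans repeated measures ANOVA with covariates and rests normality on having more than 30 subjects per group. It names no analysis set, no sensitivity analysis that includes the excluded subjects, and no method for missing data.

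**The concern.** Randomisation makes the two groups comparable at the moment of assignment. Removing subjects for something that happens later keeps that comparability only if the event is unrelated to the outcome, or if it removes the same kind of subject from both arms. Neither can be taken for granted here. Drug side effects can differ by arm because only one arm takes the active drug. ESWL complications may go with the injury the trial sets out to measure, and the trial's hypothesis is that allopurinol reduces that injury.

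The bias can run either way:

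- If complications track injury and allopurinol prevents some of them, placebo loses more of its worst cases and the benefit is understated.
- If drug side effects drive the exclusions and are related to worse outcomes, allopurinol loses more of its worst cases and a false benefit can appear.
- If the events are unrelated to the outcome, there is no bias, only fewer subjects.

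Because the rule has no time limit, a complication in week 2 would, as written, also delete urine results completed at 24 hours.

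**Working it through.** **Inputs from the documents.** 35 randomised per arm (section 1.4); significance level 0.05, taken as two-sided because the SAP does not say; normality argument requiring more than 30 per group (SAP).

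**The plan's own figure.** The 70 cannot be reproduced, because section 1.4 gives no effect size, SD, power or dropout rate. Solving backwards for two-sided 80% power with the normal approximation gives √(2/35) × (1.960 + 0.842) = 0.67 SD. With the t-test the figure is about 0.68 SD (simulated power 80.1%). I use 0.68 SD as an assumed effect.

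**The SAP's threshold.** 35 − 5 = 30, so five exclusions in one arm (5/35 = 14%) fail the SAP's own condition.

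**Assumptions for the rest.** Exclusion rates p of 5 to 20%, and a correlation r of 0 to 0.7 between the latent severity of the excluding event and the outcome (higher = worse). None of these is in the documents.

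**Mean shift.** If the worst fraction p on latent severity is excluded, the mean outcome of those retained moves by −r·φ(z)/(1−p), in SD units, where z is the (1−p) normal quantile.

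| p | z | φ(z) | φ(z)/(1−p) |
|---|---|---|---|
| 5% | 1.645 | 0.103 | 0.109 |
| 10% | 1.282 | 0.176 | 0.195 |
| 15% | 1.036 | 0.233 | 0.274 |
| 20% | 0.842 | 0.280 | 0.350 |

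The bias is r times the difference between the arms. For 15% v 5% at r = 0.5 it is 0.5 × (0.274 − 0.109) = 0.08 SD. Equal rates acting in the same way give zero.

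False-positive rates and power come from 400,000 simulated trials per case, with a pooled two-sample t-test after exclusion.

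**(1) No true effect, allopurinol losing more: false-positive rate**

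| Allopurinol v placebo excluded | r = 0 | 0.3 | 0.5 | 0.7 |
|---|---|---|---|---|
| 10% v 5% | 5.0% | 5.2% | 5.3% | 5.7% |
| 15% v 5% | 5.0% | 5.5% | 6.2% | 7.6% |
| 20% v 5% | 5.0% | 5.8% | 7.6% | 10.7% |

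The spurious differences in the last row are 0, 0.07, 0.12 and 0.17 SD.

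**(2) True effect 0.68 SD, placebo losing more: understatement and power**

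| Placebo v allopurinol excluded | r = 0 | 0.3 | 0.5 | 0.7 |
|---|---|---|---|---|
| 10% v 5%: SD | 0 | 0.03 | 0.04 | 0.06 |
| 10% v 5%: power | 76.7% | 74.5% | 73.7% | 74.1% |
| 15% v 5%: SD | 0 | 0.05 | 0.08 | 0.12 |
| 15% v 5%: power | 75.5% | 70.1% | 67.3% | 65.5% |

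For 15% v 5% the understatement is 0, 7, 12 and 17% of 0.68 SD. About 5 points of the power loss (80.1 − 75.5 = 4.6) come from smaller numbers alone.

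**(3) Allopurinol itself lowers complications.** The exclusion threshold is set by a placebo rate of 10 to 20%, and allopurinol reduces latent severity by r × 0.68. The implied allopurinol exclusions are 7–15%, 5–12% and 4–9% at r = 0.3, 0.5 and 0.7. The effect is understated by 2–4%, 6–9% and 11–17%.

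**(4) Chance that at least one arm loses five or more.** 1 − P(X₁ ≤ 4)·P(X₂ ≤ 4), with X binomial (35, p). P(X ≥ 5) is 0.029, 0.269, 0.619 and 0.857 at 5, 10, 15 and 20%. For 10% v 5%: 1 − 0.731 × 0.971 = 29%. For 15% v 5%: 63%. For 20% v 5%: 86%.

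**The case against.** The wording of the rule is not in dispute; its weight can be. Every bias figure rests on assumed rates and correlations. In the milder settings the effect is small: at most 5.7% false positives at 10% v 5%, and 2–4% understatement in case (3) at r = 0.3. The 10.7% figure is an extreme corner, and nothing in the documents links allergy or gastrointestinal upset to the urinary markers, RI or SWV. The simulation uses a t-test on one outcome, whereas the SAP plans repeated measures ANOVA; if selection acted through baseline level, within-subject comparison would cancel part of it. The trial is double-blind, which limits discretion over whom to exclude. The authors may also have wanted kidney changes unaffected by obstruction or infection.

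Most of this stands as a limit on size. The tables illustrate; they do not estimate the bias in this trial. The point of principle is untouched. Blinding does not stop true event rates differing between arms, and the planned ANOVA does not restore subjects who were removed. The documents give no rationale for the exclusions, and a wish to set aside complicated cases supports a sensitivity analysis, not the main comparison. The 30-per-group threshold is secondary: it is the SAP's own condition, not a point at which the t-test fails.

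**Conclusion.** The concern holds, and the rule must be changed. It is wrong as written, not merely short of detail: followed literally, it selects on post-randomisation events in every between-group comparison of all five outcomes, and nothing in section 1.4 or the SAP corrects for it. Confidence that the rule is there and acts this way is high. Whether it causes material bias is unknown. Under the assumptions above, the bias is nil when the events are unrelated to the outcome, small at 10% v 5%, and material only when imbalance and correlation are both larger. The plan requires no check that would show which case applies.

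**What to change.** Replace both exclusion sentences in section 1.3, and state in the SAP:

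> The primary analysis includes all randomised subjects in the group to which they were assigned, using every measurement obtained, whether or not a side effect or ESWL complication occurs.

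Then:

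- Where follow-up is still open, obtain the urine, RI and SWV measurements already scheduled for these subjects. Otherwise use those held; section 1.3 does not say that data are discarded or follow-up stopped.
- Report the restricted set only as a sensitivity analysis, since obstruction or infection may itself alter RI or the urinary markers.
- Tabulate by arm the side effects, complications, subjects removed from the restricted set, and subjects with no post-ESWL measurement.
- Repeated measures ANOVA in its usual form drops anyone with a missed visit. One way to keep them is a mixed model for repeated measures in SPSS. For each outcome, fit it to the two post-ESWL visits (2 and 24 hours for urine; two and four weeks for RI and SWV), with group, visit, group-by-visit, the baseline value and the covariates the SAP intends to control but does not name. Subjects with no post-ESWL measurement still contribute nothing to this model, which is why they are counted by arm.

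The cost is low: two protocol sentences, one SAP sentence and a table, plus a model statement if the mixed model is adopted. Complicated cases may add slightly to outcome variability, and measurements not obtained are assumed missing at random. Much of the document is in the past tense. If follow-up is over, measurements never taken cannot be recovered, and telephone contact, one of the routes in "Subjects will be evaluated when visiting the hospital according to schedule, telephone contact, or by making a home visit", cannot supply them. Reanalysis of held data and the counts by arm would still be possible. No change to clinical management is implied.

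### Subjects with the harms named in section 1.3 leave the analysis, and the SAP plans no table of harms by arm

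*Combined protocol and SAP*

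**What the plan says.** Section 1.3 of the protocol (Safety Evaluation) does two things with harms.

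- **Reporting and recording.** "If there was any drug side effects or serious adverse events(SAE), the subjects were reported to the ethics committee as soon as possible", within 24 hours of discovery. For serious events, "SAE was written in detail on the SAE form".
- **Removal from the analysis.** For drug reactions, the rule covers allergic reactions and "severe gastrointestinal disturbances (vomiting, diarrhea), the subject will be excluded from the analysis". For the procedure, "The subject will also be excluded from the analysis if the subjects experience complications related to ESWL"; the instances listed are obstruction of the ureter, pain scored above 5 on the VAS, and evidence of infection. Both lists are given as examples.

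The SAP starts with description: "Data were analysed by descriptive statistics to describe the characteristics of the subjects based on the treatment group". It then names the t-test, a chi-square test ("The categorical-scale variables used the proportion comparison with chi-square test") and repeated-measures ANOVA. It names no harm variable, safety population or table of harms. Section 1.4 plans 70 subjects, 35 of them on the intervention.

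**The concern.** A section headed as a safety evaluation gives one analysis instruction for the named events, which is to take the subject out. No other part of the plan brings these subjects back. Whether the remaining groups are still comparable for efficacy is a separate question. The issue here is the safety information itself.

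The trial gives allopurinol or placebo to limit kidney injury from ESWL. Obstruction, infection and severe pain are clinical complications of that same procedure, and allergic and gastrointestinal reactions are the likely cost of the drug. A reader of the trial report will want to know how often each occurred in each arm. Followed as written, the plan does not produce that information. It also leaves open the possibility that an absence of events in the analysed data is reported as an absence of events in the trial.

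**Working it through.** **1. Where each kind of event goes under the plan**

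| Event | Ethics report (1.3) | SAE form (1.3) | Excluded from analysis (1.3) | Tabulated by arm (SAP) |
|---|---|---|---|---|
| Allergic reaction or severe GI upset, judged a drug side effect, non-serious | Yes | No | Yes | No |
| ESWL complication, serious | Yes | Yes | Yes | No |
| ESWL complication, non-serious (for example VAS 6 pain) | Not stated | Not stated | Yes | No |
| Mild GI symptom judged a drug side effect | Yes | No | Not clearly | No |

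The last column is No throughout. The third row has no stated recording route apart from the exclusion itself.

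**2. What a summary on the analysed set would show**

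The documents state no harm rate, so there is no figure to reproduce. Let x of the 35 subjects in an arm have an event that triggers exclusion. The analysed set shows 0/(35 - x), and the randomised set shows x/35. The counts below are assumed.

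| x | Analysed set | Randomised set |
|---|---|---|
| 2 | 0/33 | 2/35 = 5.7% |
| 3 | 0/32 | 3/35 = 8.6% |
| 5 | 0/30 | 5/35 = 14.3% |
| 7 | 0/28 | 7/35 = 20.0% |
| 11 | 0/24 | 11/35 = 31.4% |

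The zero follows from the exclusion rule at any x. It arises only if the post-exclusion set is the denominator, and it covers only events that trigger exclusion.

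**3. Chance that the rule removes someone**

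For an assumed risk p per subject, P(at least one of 35) = 1 - (1 - p)^35. At p = 5% this is 83%; at 10%, 97%; at 20%, over 99%.

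**4. What a table on all 35 per arm could say**

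Take an assumed 5/35 on allopurinol and 1/35 on placebo.

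- Exact (Clopper-Pearson) 95% intervals: 14.3% (4.8 to 30.3) and 2.9% (0.1 to 14.9).
- Difference: 14.3 - 2.9 = 11.4 points.
- Newcombe interval, from the Wilson limits 6.26 to 29.38 and 0.51 to 14.53:
  - lower = 11.43 - sqrt((14.29 - 6.26)^2 + (14.53 - 2.86)^2) = 11.43 - 14.17 = -2.7;
  - upper = 11.43 + sqrt((29.38 - 14.29)^2 + (2.86 - 0.51)^2) = 11.43 + 15.27 = 26.7.
- A true 0/35 has a two-sided exact upper limit of 1 - 0.025^(1/35) = 10.0%.

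Power of a two-sided 5% test with n = 35 per arm and pooled variance under the null is Φ[(|p1 - p2| - 1.96 sqrt(2p̄(1 - p̄)/n)) / sqrt((p1(1 - p1) + p2(1 - p2))/n)], where p̄ is the mean of p1 and p2. For 5% against 20% this is Φ[(0.150 - 0.155)/0.077] = 47%. For 5% against 10% it is 12%, and for 10% against 30% it is 55%. A formal test of harm is not realistic at this size.

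**The case against.** The strongest defence is that exclusion from the analysis does not delete an event. It most naturally refers to the analysis of the urine markers, resistive index and shear wave velocity. Section 1.3 requires reporting to the ethics committee and a form for SAEs, and nothing forbids listing exclusions by arm. The trial sets no safety objective, and with 35 per arm a harms table could not settle whether the drug raises or lowers any event.

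Much of this stands, and it rules out three stronger readings that a reader might infer.

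- **That the harms are used only to remove subjects.** Section 1.3 also requires drug side effects and SAEs to be reported, and SAEs to be detailed on a form.
- **That the reported harm rate is zero by design.** No harm rate is planned and no set is named for one. The zero depends on a step that the documents do not describe, and gastrointestinal events must be severe to trigger exclusion.
- **That onset cannot be known, or that a blinded site must guess at cause before reporting.** The SAE form's contents are an open list that includes the conditions before the event. Urine sampling at 2 and 24 hours, telephone contact and home visits also allow early detection. Judging causality under blinding is ordinary practice.

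The defence does not supply a planned summary of harms by arm. Ethics reports are made case by case and do not compare arms. The chi-square sentence is not tied to any harm, and subjects with the triggering events have already left the analysis. Low power argues against testing, not against counting.

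**Conclusion.** The concern holds in a limited form. Subjects with the named drug reactions or ESWL complications are excluded from the analysis, and the SAP has no other analysis set and no harms table, so these events drop out of every planned analysis. Non-serious ESWL complications also lack a stated recording route other than exclusion.

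The size of the effect cannot be taken from the documents. Under an assumed risk of 5 to 20% per subject, at least one exclusion in an arm is likely to near certain (83% to over 99%). The assumed 5/35 against 1/35 would appear as 0/30 against 0/34 if harms were summarised on the analysed set. That last condition is an assumption about how the results might be reported and is not something the plan states. The gap should be repaired, since the remedy is cheap and specific.

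**What to change.** **SAP.** Add one descriptive safety table for all randomised subjects who took at least one dose. By arm, give the number and percentage with each event named in section 1.3, the number with any SAE, and the number excluded from the efficacy analysis with the reason. Show risk differences with 95% confidence intervals and make no significance claim. State that no event removes a subject from this table.

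**Section 1.3.** Require every named event to be recorded with its date, whatever its presumed cause or seriousness.

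**If conduct is complete.** Much of the text is in the past tense, so new recording may no longer be possible. In that case build the table from the exclusion log, the ethics reports and source records, and say that it was compiled retrospectively.

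**Cost.** One SAP paragraph, one table and a small addition to event recording, with no extra subjects or visits. The intervals will be wide at 35 per arm, and the report will show events that the current plan leaves out.
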